The National Institute of Health estimates that there will be 1,958,310 new cancer cases in 2023, of which 8.5% will be diagnosed before the age of 45. With increasing cancer cure rates and improvement in long-term survival, fertility preservation is often included as a measure of quality practice [1]. In fact, the American Society of Clinical Oncology recommends that fertility preservation should be part of the counselling for all women diagnosed with cancer in the reproductive age [2]. Many treatments for cancer, including chemotherapy, radiation therapy, and gonadal surgery are gonadotoxic and can irreversibly damage the ovarian oocyte reserve. Therefore, prior to exposure to these oncologic treatments, fertility may be preserved through several methods, one of which is in vitro fertilization (IVF) with embryo or oocyte cryopreservation [3,4]. As cancer treatment is typically urgent and time-sensitive, these patients receive timely fertility consultation and expedited IVF. In IVF, injectable gonadotropins are administered for ovarian stimulation to encourage the development of multiple ovarian follicles prior to retrieval of oocytes for cryopreservation. Gonadotropin injections include follicular stimulating hormone (FSH) with or without the addition of luteinizing hormone (LH) [5]. At our centre, for standard IVF patients, LH is often added to FSH for ovarian stimulation. However, for oncology patients undergoing IVF for cryopreservation, FSH stimulation alone is typically chosen. This difference in treatment is not evidence-based, with decision-making based on patient, financial and convenience factors. The optimal stimulation protocol for these patients has not been comprehensively studied. Accordingly, it has not been determined whether the addition of LH improves outcomes.

Physiologically, FSH is the main trophic hormone that stimulates ovarian follicle development [6]. However, LH also has several roles in follicular development and is present at low levels throughout the early follicular phase of the menstrual cycle during the time of follicular recruitment. According to the two-cell two-gonadotropin theory, LH is responsible for stimulating the ovarian thecal cells to produce androgens. Under the influence of FSH, granulosa cells use these androgens to produce estrogens, which are critical for healthy follicular development [7]. LH is also involved in ovulation induction, completion of meiosis I, and follicular luteinization and progesterone production.

In 2005, Health Canada approved the use of lutropin alfa, a recombinant human luteinizing hormone, for treatment of hypogonadotropic hypogonadism. There is growing evidence that in addition to patients with hypogonadotropic hypogonadism, patients undergoing IVF with a history of low ovarian reserve, poor ovarian response, or advanced maternal age (>35 years) may also benefit from the addition of rLH. A systematic review and meta-analysis of 40 randomized trials totaling 6443 patients undergoing IVF/ICSI using FSH and rLH versus FSH alone suggested that adding rLH to FSH resulted in a 9% increase in clinical pregnancy rates, with a 30% increase in poor responders [8]. Another meta-analysis supported the addition of rLH for patients >35 years, quoting higher pregnancy rate [9].

There has been increased interest in the fertility community of using rLH in oncology patients. In this population, the hypothalamic gonadal axis may be affected given the possible association between malignancy and a catabolic state, increase in stress hormone, and malnutrition [10,11].

Accordingly, some have suggested there may be an impact on ovarian reserve, oocyte quality, and the need for a higher dose of gonadotropins [12,13]. Currently, GnRH antagonist protocol is used as standard of care in this population to avoid delay in their cancer treatment and minimize the risk of ovarian hyperstimulation syndrome [14,15].

A cohort study by Johnson et al. [16] examined the ovarian stimulation response in oncology fertility preservation patients under various IVF stimulation protocols which included the use of rLH in some patients. The study showed no overall difference in baseline measures of ovarian reserve, total dose of gonadotropin used, or mean number of oocytes retrieved in the group of 50 chemotherapy-naïve cancer patients compared to 50 matched healthy controls. Unfortunately, the number of patients receiving rLH and the total dose received by these patients was not specified. Other studies in the literature examining rLH included case reports and case series, with sample sizes insufficient to generate conclusions regarding rLH efficacy in cancer patients [17-19]. A systematic review concluded that research on ovarian stimulation protocols and outcomes in the onco-fertility literature was inconsistent and of low quality [20], calling for higher quality studies to provide clarity on this topic.

Therefore, we intend to conduct an exploratory randomized controlled trial (RCT) comparing FSH and LH versus FSH alone using a GnRH antagonist protocol in non-hormone sensitive cancer patients undergoing fertility preservation. These patients include those diagnosed with malignancy other than breast, uterine and ovarian cancer.

3. Study Question

In non-hormone sensitive cancer patients undergoing IVF fertility preservation, does the use of FSH and LH for ovarian stimulation lead to a greater proportion of mature oocytes available for cryopreservation relative to AFC compared to FSH alone?

We theorize that supplementation with FSH + rLH will increase the yield of mature MII oocytes among patients with non-hormone sensitive cancer undergoing fertility preservation compared to those with FSH alone. In addition, we anticipate the following trends among patients in the FSH + rLH group compared to those supplemented with FSH alone:

- Higher number of total oocytes retrieved per cycle
- Higher "Follicular Output Rate" (FORT), defined as ratio of pre-ovulatory follicles (16-22mm) on day of trigger divided by AFC [22]
- Higher number of cryopreserved embryos (if patient chooses to freeze embryos rather than oocytes)
- No significant difference in incidence of moderate-severe OHSS

5. Rationale

Fertility preservation is performed before the initiation of cancer therapy in an effort to reduce its cytotoxic effects on ovarian function. However, recent literature has demonstrated that ovarian function is reduced in cancer patients even before starting cancer treatment. A case series reported a greater proportion of immature oocytes per cycle and lower maximal levels of estradiol in various cancer patients compared to patients with isolated tubal infertility, suggesting the negative impact

of cancer on oocyte maturation [12]. A matched cohort study reported lower AMH levels in patients with lymphoma before chemotherapy, warranting higher doses of gonadotropins for ovarian stimulation to maximize the number of oocytes retrieved before chemotherapy [13].

Studies have highlighted that administration of exogenous FSH and LH is essential for patients with hypogonadotropic hypogonadism [23], which is consistent with the current approved use of rLH by Health Canada. Evidence also supports the use of rLH in poor responders with advanced maternal age [9]. There is growing concern in the literature that some oncology patients may be poor responders prior to cancer therapy due to hypothalamic gonadal axis dysfunction secondary to their malignancy [2]. With evidence suggesting that the hypothalamic gonadal axis is affected in the oncology population, and that rLH may improve fertility preservation outcomes in a subgroup of patients that mimic hypogonadotropic cases, the efficacy of rLH in oncology patients is plausible.

Given the mixed literature of rLH efficacy in the oncology population and the improved fertility preservation outcomes in various patients supplementing ovarian stimulation with rLH, an exploratory randomized controlled trial is warranted to definitively address the safety and efficacy of rLH in non-hormone sensitive cancer patients.

6. Significance of the study

Managing onco-fertility patients poses a special challenge for the IVF physician. After patients undergo treatment for their underlying cancer with surgery, chemotherapy, and/or radiotherapy, they may demonstrate premature ovarian failure at an early stage of life. Ovarian failure following cancer therapy is particularly significant considering the already compromised fertility of cancer patients. Previous systematic reviews have highlighted the need for higher quality studies evaluating ovarian stimulation in cancer patients [20]. Results of this trial will have immense impact on the future practice of reproductive medicine. In the instance of rLH and FSH demonstrating superiority compared to FSH alone, future patients will have improved fertility preservation outcomes and corresponding greater quality of life knowing the improved success of future biological pregnancy. In the instance of rLH and FSH demonstrating no significant difference compared to FSH alone, IVF physicians will counsel patients regarding the lack of benefit of rLH and accordingly reduce the costs associated with assisted reproductive technology.

7. Study objectives

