7.6 Outcome measures

The primary outcome measure will be the total number of mature (MII) oocytes adjusted by antral follicle count (AFC) available for cryopreservation.

Secondary outcome measures will include the following:

- Total number of oocytes retrieved per cycle
- Ratio of mature (MII) to immature oocytes
- Total number of mature oocytes (MII) retrieved per IVF/ICSI cycle
- Oocyte yield (defined as the number of metaphase II (MII) oocytes retrieved divided by the number of follicles ≥15 mm on ultrasound on the day of trigger)
- "Follicular Output Rate" (FORT) (defined as ratio of pre-ovulatory follicles (16-22mm) on day of trigger × 100/AFC (3-8mm) [22]
- Incidence of moderate to critical OHSS based on the classification criteria by Golan et al [26].
- If the embryos are frozen:
 - o Fertilization rate, which will include two outcomes each defined as follows:
 - Definition 1: number of 2PN zygotes divided by the number of mature oocyte(s) fertilized per IVF/ICSI cycle.
 - Definition 2: number of 2PN zygotes divided by the number of oocytes incubated with at least 10,000 sperm per IVF cycle.
 - Total number of good quality day 5 embryos available for cryopreservation determined by an embryologist using the classification system by Gardner and Schoolcraft, 1999 [25].
- Dose-adjusted evaluation of the safety and tolerability of follitropin alfa + lutropin alfa compared to follitropin alfa as measured by incidence of:
 - o Treatment-emergent adverse events (TEAEs)
 - Treatment-related adverse events (AEs)
 - o Incidence of thromboembolic events

8. Study methods

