9.1 Discontinuation criteria and safety parameters

All patients undergoing a treatment of IVF at Mount Sinai Fertility are screened to ensure that they are in good health before starting a treatment cycle. All of our patients will be receiving a GnRH antagonist protocol which has lower rates of OHSS [27]. In addition, all patients in this study will have a freeze-all cycle, which will further minimize the risk of developing OHSS. There are preestablished protocols to monitor and minimize the risk of OHSS for any patient undergoing fertility treatment, including cycle cancellation prior to trigger, coasting, and/or administration of a dopamine agonist. All study participants will be extensively counselled about signs and symptoms of severe OHSS and advised to seek medical attention should they experience such signs or symptoms.

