12.1 Sample Size

A sample size calculation was performed according to the primary outcome of the total number of mature oocytes available for cryopreservation [28]. We assume the control group will have a mean of 8 cryopreserved oocytes with a standard deviation of 4 according to data from a previous meta-analysis of randomized trials evaluating FSH and LH versus FSH alone using a GnRH antagonist protocol [29]. We will use an alpha level of 5%, power of 80%, enrolment ratio of 1, and assume a 20% improvement in FSH and LSH versus FSH alone. This calculation will yield a sample size of 126 patients (n=63 per group). Accounting for 10% loss to follow-up, the total sample size will be 140 patients (n=70 per group). Reported p-values will be recorded as two-tailed. The following formula was used for sample size calculation, which was doubled to account for two trial arms and multiplied by 1.1 to account for 10% loss to follow-up:

$$n_1 = \frac{(\sigma_1^2 + \sigma_2^2/K)(Z_{1-\frac{\alpha}{2}} + Z_{1-\beta})^2}{|u_2 - u_1|^2}$$

$$n_1 = \frac{(4^2 + 4^2/1)(1.96 + 0.84)^2}{|10 - 8|^2}$$

$$n = 63 * 2 * 1.1$$

Where n_1 is the sample size for the FSH and LH group; σ_1^2 is the variance for FSH and LH group; σ_2^2 is the variance for the FSH only group; $Z_{1-\frac{\alpha}{2}}$ is the Z-score corresponding to an alpha level of 0.05; $Z_{1-\beta}$ is the Z-score corresponding to a power of 0.80; u_1 is the projected mean number of cryopreserved oocytes in the FSH and LH group; u_2 is the projected mean number of cryopreserved oocytes in the FSH only group; n is the total sample size after accounting for projected loss to follow-up

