12.2 Planned analysis

The analysis will be performed on an intention-to-treat principle. Continuous variables will be examined for normality using a normal probability plot. Normally distributed continuous variables will be compared using Welch's t-test. Continuous variables not normally distributed will be compared using Mann-Whitney U test. Categorical data will be reported as counts with percentage, and compared with chi-square test or Fisher's exact test whenever appropriate. Additional sensitivity analysis will be performed taking into account potential confounding factors (i.e. Age, AMH, AFC). Regression analysis with age and FSH dose as factors will also be performed. Statistical analysis will be performed using R statistical software (R Foundation for Statistical Computing).

13. Trial registration

The clinical trial will be registered and available online at www.clinicaltrials.gov once the protocol is approved by the Mount Sinai Hospital Research Ethics Board.

14. Knowledge translation

The lack of consensus on the safety and efficacy of rLH in addition to FSH for ovarian stimulation calls for high quality randomized trials. Once the trial is completed and results are available, knowledge translation is of critical importance and involves the translation of findings to policy and practice [30]. Several procedures will be implemented to share the results of this trial internationally given the increasing number of young patients diagnosed with cancer. The study results will be firstly presented at international fertility conferences. The results will also be published in a high impact fertility journal, such as *Human Reproduction*. Experts in the field will be contacted to ensure they are aware of trial results.

15. Role of principal investigator

[name] is a reproductive endocrinologist at Mount Sinai Fertility as well as a Professor in the Department of Obstetrics and Gynecology at Mount Sinai Hospital. She will be supervising all aspects of the trial.

16. References

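### A non-significant OHSS comparison in a trial sized on oocyte count cannot show that rLH adds no OHSS risk, nor settle its safety definitively

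*Protocol*

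**What the plan says.** The hypotheses that follow section 3 (Study Question) open with mature oocyte yield and then add a list under the words "we anticipate the following trends among patients in the FSH + rLH group compared to those supplemented with FSH alone". The last item in that list is "No significant difference in incidence of moderate-severe OHSS".

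Section 5 (Rationale) concludes that "an exploratory randomized controlled trial is warranted to definitively address the safety and efficacy of rLH in non-hormone sensitive cancer patients".

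Section 7.6 makes OHSS a secondary outcome: "Incidence of moderate to critical OHSS based on the classification criteria". No expected rate is given there or elsewhere. Section 9.1 indicates that few events are likely: all patients receive a GnRH antagonist protocol, and "all patients in this study will have a freeze-all cycle, which will further minimize the risk of developing OHSS".

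Section 12.1 bases the number of patients on another outcome: "A sample size calculation was performed according to the primary outcome of the total number of mature oocytes available for cryopreservation". The result is 63 evaluable and 70 enrolled per arm. Under section 12.2, categorical data are given as counts and percentages and "compared with chi-square test or Fisher's exact test whenever appropriate". The protocol sets no margin for OHSS and no size of increase that the trial should be able to exclude.

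**The concern.** The OHSS expectation is worded as a test result, and the result it expects is non-significance. A trial with few events tends to give that result whether or not the added drug raises the risk. The small sample thus works in favour of the stated expectation, whereas for the oocyte outcomes it works against it.

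The Rationale then claims that the trial will settle safety definitively, in the same sentence that calls it exploratory. Section 10 describes OHSS as the most serious side effect reported for the study drug. If a non-significant comparison were taken at face value, patients and clinicians could be told that rLH adds no OHSS risk when the data still allowed a several-fold increase.

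**Working it through.** **1. The plan's own figure.** Section 12.1 uses SD 4 in both arms, a difference of 10 − 8 = 2, two-sided alpha 5% and power 80%:

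n per arm = (4² + 4²)(1.96 + 0.84)² / 2² = 32 × 7.84 / 4 = 62.72, rounded up to 63.

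Total = 126, and 126 / 0.90 = 140. The stated numbers reproduce with the difference of 2 that stands in the formula. No term in the calculation concerns OHSS.

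**2. Thresholds that need no assumed rate** (70 per arm, two-sided Fisher test at 0.05).

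- 5 cases on rLH against 0 on control: p = 2 × C(70,5)/C(140,5) = 2 × 0.0290 = 0.058, not significant.
- 6 against 0: p = 2 × C(70,6)/C(140,6) = 2 × 0.0140 = 0.028, significant.
- With 1 control case, at least 8 rLH cases are needed (7 against 1: p = 0.063; 8 against 1: p = 0.033).

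So 5 against 0 would satisfy the stated expectation if Fisher's test is used. Uncorrected chi-square would give p = 0.023 for the same table, but the expected count is only 2.5 cases per arm, a situation in which Fisher's test is normally preferred.

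**3. Power for a true increase.** The protocol gives no OHSS rate, so the control rates are assumptions. Power is the sum of the binomial probabilities of all tables with p ≤ 0.05, at 63 and at 70 per arm.

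| Control vs rLH | Fisher | Uncorrected chi-square |
|---|---|---|
| 2% vs 4% | 1–2% | 8–9% |
| 3% vs 6% | 4–5% | 11–13% |
| 5% vs 10% | 10–11% | 18–20% |
| 2% vs 6% | 6–8% | 19–21% |
| 3% vs 9% | 15–18% | 29–32% |
| 5% vs 15% | 35–41% | 48–52% |
| 10% vs 30% | 76–81% | 82–86% |
| 5% vs 25% | 87–91% | 91–94% |

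For control rates of 2% to 5%, a tripling would be missed in about 59% to 94% of trials by Fisher's test and about 48% to 81% by uncorrected chi-square. A doubling would be missed in about 80% or more by either test.

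**4. What the data could exclude.**

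- 0 cases in 70: exact two-sided 95% upper limit = 1 − 0.025^(1/70) = 0.0513, or 5.1%.
- 1 case in each arm of 70: Newcombe 95% interval for the risk difference of about −6.3 to +6.3 percentage points.

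**5. For scale.** Detecting a doubling with 80% power (normal approximation, two-sided 5%) would need 1,141 patients per arm at a control rate of 2%, 749 at 3% and 435 at 5%.

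**The case against.** The strongest reply is that the OHSS line is an anticipated trend, not a formal hypothesis. OHSS is a secondary outcome in a trial described as exploratory, and low power for a rare safety event is normal when a trial is sized on efficacy. Incidence by arm is already planned as counts and percentages, and a confidence interval could properly come from a statistical analysis plan. The word on definitive safety evidence stands in the background text and changes no test or data item. Safety in section 7.6 also covers adverse events and thromboembolism, which the OHSS figures do not measure.

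Much of this stands. Low power for OHSS is not an error in itself, and the lack of a stated interval is no finding. But a non-significant difference is a test outcome and not a trend, and an analysis plan cannot correct an expectation and a claim made in the protocol. The exploratory label is no defence when the same sentence promises a definitive answer.

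Three stronger readings are not supported:

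- A reader might infer that the expectation would be met almost whatever the true risk. It would not: 5% against 25% is detected with 87–91% power by Fisher's test, and 10% against 30% with 76–81%.
- A reader might take the miss rates as properties of the design alone. They depend on assumed control rates and on which of the two permitted tests is used.
- A reader might infer that the protocol commits to reporting non-significance as proof of equal risk. It does not say so. Section 6 reads a non-significant result as lack of benefit, but only for efficacy.

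**Conclusion.** The point holds in limited form, and the text is wrong as written. The protocol claims definitive safety evidence, which its design cannot provide, and it states an OHSS expectation that low power alone could satisfy. At 63 to 70 per arm and an assumed control rate of 2% to 5%, the trial has at best about even odds of detecting a tripled OHSS risk, and by Fisher's test 41% at most. The conclusion would weaken if the true control rate were near 10% or the increase very large. It does not depend on the assumed rates for the event thresholds or the 5.1% upper limit. The sample size for the primary outcome and the primary analysis are unaffected.

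**What to change.** Three changes of wording:

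1. Replace the OHSS expectation with an estimation aim: OHSS incidence in each arm, and the risk difference with a 95% confidence interval by a method suited to sparse data.
2. State that no conclusion of equal OHSS risk will be drawn from a non-significant test.
3. In the Rationale, replace the claim to address safety and efficacy definitively with one to provide initial randomised estimates of the safety and efficacy of rLH in this population.

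No additional patients, visits or data are needed. The cost is a more modest safety claim. If the sponsor wants to conclude that a given increase in OHSS has been excluded, a margin would have to be justified and the trial sized for it. As an illustration only, with a 5-point margin, equal true rates, one-sided 2.5% and 80% power, that needs 124 per arm at a 2% rate and 299 per arm at 5%.

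### Section 6 reads a non-significant result as lack of benefit of rLH, which a superiority trial with 80% power cannot show by non-significance alone

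*Protocol*

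**What the plan says.** Protocol section 6 (Significance of the study) gives two scenarios. If the combination is superior, future patients gain. The other scenario is a trial "demonstrating no significant difference compared to FSH alone, IVF physicians will counsel patients regarding the lack of benefit of rLH", with savings in treatment cost to follow. No estimate, interval or inconclusive outcome is mentioned there, and no other part of the protocol says how a null efficacy result would be read.

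The rest of the design is a superiority trial:

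- The hypothesis, stated after the study question in section 3, is directional: "We theorize that supplementation with FSH + rLH will increase the yield of mature MII oocytes".
- Section 12.1 sets the error rates: "We will use an alpha level of 5%, power of 80%, enrolment ratio of 1", and "Reported p-values will be recorded as two-tailed". The planning values are a control "mean of 8 cryopreserved oocytes with a standard deviation of 4" and, in the formula, means of 10 and 8.
- Section 12.2 compares continuous outcomes by Welch's t-test if normal; otherwise, "Continuous variables not normally distributed will be compared using Mann-Whitney U test". Both are tests of difference.

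The protocol calls the trial exploratory in several places. Section 5 (Rationale) nevertheless says that "an exploratory randomized controlled trial is warranted to definitively address the safety and efficacy of rLH".

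**The concern.** Failing to reject equality is not evidence of equality. A trial planned with 80% power accepts a one-in-five chance of missing the very difference it was planned for. When it misses, the data may still be compatible with that difference. The second scenario in section 6 does not separate a null result whose interval rules out the planned gain from one whose interval includes it. Both would be passed to patients as showing that rLH does not help.

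What is at stake is the conclusion and the counselling that rests on it. The tests, the type I error rate and the sample size are not affected.

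**Working it through.** **Inputs, all from section 12.1:** SD 4 in each arm, two-sided alpha 5%, power 80%, 1:1 allocation, difference 10 − 8 = 2 oocytes, 63 per arm evaluable, 70 per arm enrolled. The scale is the raw oocyte count. The primary outcome in section 7.6 is the MII count adjusted by AFC, for which no SD is given, so everything below illustrates the point on the sizing scale only.

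**The plan's own figure.** n per arm = (4² + 4²)(1.96 + 0.84)² / 2² = 32 × 7.84 / 4 = 62.72, rounded up to 63, or 126 in total. 126 / 0.90 = 140. The stated 63, 126 and 140 are reproduced for a difference of 2.

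**Precision at 63 per arm** (normal approximation).
- SE = 4 × √(2/63) = 0.713.
- 95% CI half-width = 1.96 × 0.713 = 1.397.
- The result is non-significant when the observed difference lies between −1.397 and +1.397.
- The highest upper limit of a non-significant result is 2 × 1.397 = 2.79.
- The interval includes 2 whenever the observed difference exceeds 2 − 1.397 = 0.603.

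So any observed gain between 0.603 and 1.397 oocytes is non-significant and also compatible with the gain used for sizing. For example, an observed gain of 1.0 has an interval from 1.0 − 1.4 = −0.4 to 1.0 + 1.4 = 2.4.

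**How often this could arise.**

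| | 63 per arm | 70 per arm |
|---|---|---|
| SE | 0.713 | 0.676 |
| CI half-width | 1.40 | 1.33 |
| True gain 2: probability of a non-significant result | 19.9% | 15.9% |
| No true effect: share of non-significant results whose CI includes 2 | 0.174 / 0.950 = 18% | 0.134 / 0.950 = 14% |
| No true effect: probability that the CI upper limit is below 2 | 80% | 84% |

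A simulation with skewed counts (negative binomial, mean 8, SD 4, 63 per arm, Welch's test, 4,000 runs) gave similar values: 21.6% non-significant at a true gain of 2, and 18.5% of null intervals including 2 when there is no effect.

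The table cuts both ways. If rLH does nothing, most null results would be informative about a 2-oocyte gain. A minority would not be, and a p-value above 0.05 does not tell a reader which kind is at hand.

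**The case against.** The strongest reply is that section 6 is background text about expected impact. It predicts what physicians will do and fixes no hypothesis, test, margin or reporting rule. This stands, and it limits the weight of the point. It also rules out several stronger readings that a reader might infer:

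- *Section 6 is a decision rule that produces a 20% rate of false conclusions.* The documents do not support this. The 20% is the ordinary type II error of any trial with 80% power; section 6 does not create it. Nothing says that section 6 governs reporting.
- *The plan lacks an interval rule or a margin.* The statistical analysis plan is not at hand and may hold one. Its absence from the protocol is no finding.
- *Any interval-based rule in the analysis plan would contradict section 6.* This goes too far. Such a rule could simply qualify or supersede a sentence of rationale, and many null results would satisfy both.
- *The planned difference is the smallest worthwhile benefit, so a formal margin must be built on it.* The protocol never says that it is.
- *The Rationale's claim to settle efficacy cancels the exploratory label.* The same sentence contains both, so it cannot settle the matter either way. If the trial is exploratory, a firm negative conclusion is harder to justify, not easier.

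The reply does not remove the defect. The sentence is the only interpretation of a null efficacy result on record, it names what patients would be told, and the inference is invalid on any outcome scale.

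**Conclusion.** The point holds as a matter of interpretation. Section 6 equates non-significance with lack of benefit, and a superiority design with 80% power analysed by difference tests does not license that step. On the raw-count inputs with 63 per arm, a non-significant result can leave gains of up to about 2.8 oocytes inside the 95% confidence interval, including the 2 oocytes used for sizing.

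The sizes rest on SD 4 in both arms, a normal approximation, and the raw count in place of the AFC-adjusted outcome. The logic does not depend on them. Severity is low within the minor range, because analysis and sample size stay as they are.

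Two neighbouring matters are separate. Section 12.1 says in words "assume a 20% improvement in FSH and LSH versus FSH alone", which is 0.20 × 8 = 1.6 oocytes, whereas its formula uses 2. Whether a formal margin should be set on the AFC-adjusted scale is also a different question.

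**What to change.** In section 6, replace *the lack of benefit* with *no evidence of benefit*, and add a sentence along these lines: *A non-significant result will be reported with the estimated treatment difference and its 95% confidence interval, and will be treated as inconclusive where that interval still includes the improvement the trial was sized to detect.*

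The added sentence relies on that improvement being stated once and consistently. If it cannot yet be expressed on the AFC-adjusted scale, the change of wording together with the estimate and interval is still worth making. The choice of interval method can be left to the analysis plan.

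The cost is an edit to one paragraph, with no change to tests, sample size or conduct. The real downside is that some null results must be called inconclusive: on the raw count with no true effect, about 18% of them for a gain of 2 at 63 per arm, or 14% if all 70 per arm are analysed.
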